### 1.4 Objectives

**Primary Objective:** To investigate the effect of crisaborole (Eucrisa™) treatment on patient-reported itch and pain in patients with mild to moderate atopic dermatitis compared to tacrolimus 0.03%.

- *Hypothesis:* We hypothesize that crisaborole (Eucrisa™) treatment will significantly decrease (i.e., score change  $\geq 5$ ) the severity of itch and pain over time and these changes will correlate with improvements Eczema Area and Severity Index (EASI) in atopic dermatitis. We further hypothesize that the improvement in these PROs will be greater in the crisaborole treated subjects compared to those receiving tacrolimus.
- *Primary Outcome Measures:* Change in PROMIS® Itch and PROMIS® Pain Interference measures after 12 weeks of treatment.

**Secondary Objective:** To investigate the effect of crisaborole (Eucrisa™) treatment on patient-reported quality of life, sleep, anxiety, and depression in patients with mild to moderate atopic dermatitis compared to tacrolimus 0.03%.

- *Hypothesis:* We hypothesize that crisaborole (Eucrisa™) treatment will improve quality of life and decrease (i.e., score change  $\geq 5$ ) the severity of one or more of the PROs (sleep, anxiety, or depression). These changes will correlate with improvements in atopic dermatitis (EASI). We also hypothesize that the improvement in these PROs will be greater in the crisaborole treated subjects compared to those receiving tacrolimus.
- *Secondary Outcome Measures:* Change in Children’s Dermatology Life Quality Index (CDLQI), PROMIS® Anxiety, PROMIS® Depression, and Children’s Sleep Habits Questionnaire (CSHQ) after 12 weeks of treatment.

**Tertiary Objective:** To elucidate the impact of crisaborole (Eucrisa™) treatment or tacrolimus 0.03% on caregiver burden.

- *Hypothesis:* We hypothesize that improvements in caregiver burden will correlate with improvements in atopic dermatitis (EASI), as well as decreased severity in PROs.
- *Tertiary Outcome Measures:* Change in Caregiver Burden Inventory and Family Dermatology Life Quality Index (FDLQI) after 12 weeks of treatment.

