### **11. DATA ANALYSES AND MONITORING**

#### **11.1. Sample Size Determination**

We will accrue 48 patient and caregiver pairs, accounting for 20% withdrawal or dropout rate, to ensure evaluation of 40 patient and caregiver pairs (i.e., 20 per AD patient/caregiver pairs per topical treatment). All statistical tests will be performed at the two-tailed 0.05 level of significance. For an effect size of 5.0 in a population with standard deviation of 10.0, a sample size of 16 will provide 80% power to detect a score change of 4 in the two primary outcome measures. An electronic medical record search for the last year counted 900 patients with the diagnosis of atopic dermatitis between the ages of 1 and 17 years. However, it is unclear how many of these patients have mild or moderate AD. We will enroll a total of 40 evaluable patients and caregivers (i.e., 20 per AD treatment; 80 total participants). Our sample size will allow us to detect a change of at least 4 (i.e., clinically significant change) in the itch and pain PROs between baseline and 12 weeks of treatment. Subjects that complete at least the 6 week assessment will be considered evaluable. In this study, the superiority of crisaborole is not dependent on the clinical change (EASI); superiority is dependent on significant changes in PROs and their potential correlation with EASI. Therefore, crisaborole would be superior to tacrolimus if crisaborole improves PROs (and/or caregiver burden), but its clinical effectiveness (EASI) is not statistically significantly different than tacrolimus.

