#### **11.2. Planned Statistical Analyses**

All statistical analyses will be performed at a two-tailed 0.05 level of significance. Descriptive statistics will be performed using the demographic information (i.e., gender, age, race, ethnicity, disease severity) to characterize the patient and caregiver population at baseline. Descriptive statistics will also be utilized to identify PROs most affected by AD and the extent of caregiver burden related to AD. Primary analyses will use ANCOVA, correlative analyses, and regression analyses to identify significant changes in itch or pain interference from baseline to 12 weeks (Baseline Assessment to Treatment Assessment #2). Longitudinal analyses will be performed to examine changes in itch and pain interference over time. Additionally, we will determine the association between itch and pain interference at baseline and over time. Furthermore, we will correlate change in severity of itch and pain interference with change in %BSA of treatable AD. Two-tailed t-tests will compare changes in itch and pain interference between crisaborole and tacrolimus. Secondary and tertiary analyses will employ similar statistical methodology as the primary analyses but to anxiety, depression, sleep, quality of life, and caregiver burden.

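### The Section 11.1 superiority rule does not say which or how many outcomes carry the claim, controls error only per test, and uses a non-significant EASI difference with no margin

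*Combined protocol and SAP*

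**What the plan says.** Section 11.1 is the only place where the plan defines superiority. It says crisaborole "would be superior to tacrolimus if crisaborole improves PROs (and/or caregiver burden), but its clinical effectiveness (EASI) is not statistically significantly different than tacrolimus". Just before that, it says that "the superiority of crisaborole is not dependent on the clinical change (EASI"), and then that "superiority is dependent on significant changes in PROs and their potential correlation with EASI".

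Section 1.4 ranks eight measures:
- two primary: PROMIS Itch and PROMIS Pain Interference;
- four secondary: CDLQI, PROMIS Anxiety, PROMIS Depression and CSHQ;
- two tertiary: Caregiver Burden Inventory (CBI) and FDLQI.

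Its primary and secondary hypotheses include the expectation that "improvement in these PROs will be greater in the crisaborole treated subjects compared to those receiving tacrolimus". Section 11.2 plans the matching test: "Two-tailed t-tests will compare changes in itch and pain interference between crisaborole and tacrolimus". Similar methods are to be used for the other outcomes. On error control, Section 11.2 says "All statistical analyses will be performed at a two-tailed 0.05 level of significance", and Section 11.1 says the same of all tests. Neither gives an adjustment, a testing order or a co-primary rule. The one severity correlate that Section 11.2 names is %BSA: "we will correlate change in severity of itch and pain interference with change in %BSA of treatable AD".

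**The concern.** A superiority rule should let two readers with the same results reach the same conclusion. This one does not, for three reasons.

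1. **Which outcomes, and how many.** The rule speaks of PROs in general and does not use the ranking in Section 1.4. Naming two primaries does not settle whether either or both must succeed: Section 1.4 joins itch and pain with "and", while Section 11.2 joins them with "or". The and/or wording lets caregiver burden, a tertiary outcome, carry the claim alone.
2. **Error rate.** With 0.05 for each test and an open choice among eight measures, the chance of a false claim depends on a choice that can be made after the data are seen. The trial is open-label.
3. **EASI.** Superiority is said not to depend on EASI, then to depend on a potential correlation with EASI, and then to go with a non-significant EASI difference. No margin is given. Read literally, the rule fails if crisaborole is also significantly better on EASI.

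At stake is the comparative conclusion. Section 2.1 says the trial will be able to determine whether crisaborole is the better overall treatment.

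**Working it through.** **Inputs.** From the documents: two-sided 0.05 per test (11.1, 11.2); 20 evaluable pairs per arm and SD 10 (11.1); a change of 5 (1.4, 11.1); eight ranked measures (1.4). Assumed, because the documents give no figure: correlation of 0 to 0.5 between outcomes, and an SD of change equal to the stated SD of 10.

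**The plan's own figures.** The plan gives no error rate for the rule, so there is none to reproduce. Its sample size of 16 for 80% power does not reproduce for a change from baseline: (10 × (1.96 + 0.84) / 5)² = 31.4, so 32, and 50 for a change of 4. That is a separate matter and nothing below depends on it.

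**False claim for crisaborole, identical drugs, between-arm tests.** Each test favours crisaborole falsely with probability 0.025. The EASI test is non-significant with probability 0.95.

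Independent outcomes, exact:
- either primary: (1 − 0.975²) × 0.95 = 0.0494 × 0.95 = 0.047;
- CBI or FDLQI alone: the same, 0.047;
- any of eight: (1 − 0.975⁸) × 0.95 = 0.1833 × 0.95 = 0.174;
- both primaries: 0.025² × 0.95 = 0.0006.

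Correlation 0.5, by simulation:
- either primary about 0.039;
- caregiver measures alone about 0.038;
- any of eight about 0.11;
- both primaries about 0.003.

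Counting errors in either direction and ignoring EASI, independent tests give 1 − 0.95² = 0.0975 for two and 1 − 0.95⁸ = 0.337 for eight.

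**EASI clause.** A two-sample t-test at two-sided 0.05 with 20 per arm has power 0.338 for a true difference of 0.5 SD. A deficit of that size would be non-significant with probability 1 − 0.338 = 0.662.

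**Power of the two possible rules** (5 points better on both primaries, SD of change 10, 20 per arm, t-test):
- single test: 0.338 at 0.05 and 0.238 at 0.025, the first Holm step;
- at least one primary, unadjusted: 0.560 (correlation 0) to 0.492 (correlation 0.5);
- at least one primary, Holm: 0.419 to 0.368;
- both primaries at 0.05: 0.338² = 0.114 at correlation 0. At correlation 0.5, 2 × 0.338 − 0.492 = 0.184.

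Children under 5 give no self-report (5.1). If ages are spread evenly over 2 to 15, 20 × 11/14 = 15.7 per arm supply the primaries. At 16 per arm the single-test figures are 0.278 and 0.188. The false-claim rates hardly change, because the t-tests keep their size.

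**The case against.** The strongest reply is that the comparison is not really in doubt. The sentence itself names tacrolimus, Section 1.2 expects an effect superior to that of tacrolimus, Section 1.4 hypothesises greater improvement than on tacrolimus, and Section 11.2 plans between-arm t-tests. This stands. A reader might infer that the trial has no between-arm comparison, or that any improvement from baseline on crisaborole alone would count as superiority. The documents do not support either: the between-arm meaning is the natural one. What remains is narrower. The sample size in Section 11.1 and the analyses labelled primary in Section 11.2 are framed as change from baseline, so the rule should state its contrast.

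A second reply is that the inflation is modest once the ranking in Section 1.4 is respected: 4–5% for either primary, and under 0.5% if both are needed, which requires no adjustment. This also stands, and the upper figure of 17% applies only if any measure may carry the claim. But the wording of the rule allows exactly that, and names caregiver burden expressly.

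A third reply is that adjusting secondary and tertiary outcomes in a 40-pair open-label study is a matter of preference. That is fair. Those outcomes need no adjustment if they carry no superiority claim.

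Finally, Section 2.1 does not cite the Section 11.1 rule, so that the rule decides the question of the better overall treatment is an inference. Section 11.2 also lists unspecified correlative analyses, so an EASI correlation is unnamed rather than excluded.

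**Conclusion.** The concern holds for the decision rule and should be fixed before analysis. Applied as worded to between-arm comparisons, with no true difference, the rule gives a false crisaborole claim about 4–5% of the time if either primary suffices and about 11–17% if any of eight measures suffices, against a nominal 2.5%. The ranges rest on an assumed correlation of 0 to 0.5; the upper ends are exact for independent outcomes. The EASI clause contradicts the statement before it and cannot support equal effectiveness, since a 0.5 SD deficit would go undetected about two times in three at 20 per arm. The finding is not that the trial lacks a comparator or a between-arm test. It is that the rule is not linked to the ones the plan has.

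**What to change.** In Section 11.1, state that superiority is claimed on the between-arm difference in change from baseline to week 12 in PROMIS Itch and PROMIS Pain Interference. Choose one of these before analysis:

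- **(i)** at least one primary favours crisaborole, with Holm adjustment at overall two-sided 0.05, and the claim is limited to the outcome or outcomes that succeed; or
- **(ii)** both favour crisaborole, each at two-sided 0.05, without adjustment.

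Name one between-arm test from those already in Section 11.2, the t-test or the ANCOVA. Say how children with only the 6-week assessment, whom Section 11.1 counts as evaluable, enter the week 12 comparison. Make the other PROs and the caregiver measures supportive. Report the between-arm EASI difference with a 95% confidence interval, neither as a condition for superiority nor as evidence of equal effectiveness. In Section 11.2, name the correlation of PRO change with EASI change, on which Sections 1.4 and 11.1 rely. Use one score-change threshold: Sections 1.4 and 5.3 use 5, while Section 11.1 uses 4.

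**Cost.** Rewording, plus some power. Under (i) with the t-test, per-test power for 5 points falls from about 34% to 24% at 20 per arm (28% to 19% at 16), and the chance that at least one primary succeeds falls from 49–56% to 37–42% at 20 per arm. ANCOVA would recover part of this: about 32% per test at 0.025 and 20 per arm, if baseline and week 12 scores correlate 0.5 (assumed). Option (ii) needs no alpha split but gives only about an 11–18% chance of a claim at 20 per arm. Low between-arm power is already in the plan and is a separate matter.

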#### **11.2. Planned Statistical Analyses**

All statistical analyses will be performed at a two-tailed 0.05 level of significance. Descriptive statistics will be performed using the demographic information (i.e., gender, age, race, ethnicity, disease severity) to characterize the patient and caregiver population at baseline. Descriptive statistics will also be utilized to identify PROs most affected by AD and the extent of caregiver burden related to AD. Primary analyses will use ANCOVA, correlative analyses, and regression analyses to identify significant changes in itch or pain interference from baseline to 12 weeks (Baseline Assessment to Treatment Assessment #2). Longitudinal analyses will be performed to examine changes in itch and pain interference over time. Additionally, we will determine the association between itch and pain interference at baseline and over time. Furthermore, we will correlate change in severity of itch and pain interference with change in %BSA of treatable AD. Two-tailed t-tests will compare changes in itch and pain interference between crisaborole and tacrolimus. Secondary and tertiary analyses will employ similar statistical methodology as the primary analyses but to anxiety, depression, sleep, quality of life, and caregiver burden.

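### Section 11.2 names change in %BSA as the only clinical correlate, while all three hypotheses in section 1.4 predict correlation with EASI

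*Combined protocol and SAP*

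**What the plan says.** Section 1.4 gives three hypotheses, and each names EASI as the clinical correlate:

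- Primary (itch and pain): "these changes will correlate with improvements Eczema Area and Severity Index (EASI) in atopic dermatitis".
- Secondary (quality of life, sleep, anxiety, depression): "These changes will correlate with improvements in atopic dermatitis (EASI".
- Tertiary (caregivers): "improvements in caregiver burden will correlate with improvements in atopic dermatitis (EASI".

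Section 11.1 says that "the superiority of crisaborole is not dependent on the clinical change (EASI", and then that "superiority is dependent on significant changes in PROs and their potential correlation with EASI". Its closing sentence would call crisaborole superior if it improves the patient-reported outcomes (PROs) or caregiver burden while EASI does not differ significantly between the arms.

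Section 11.2, which sets out the analyses, states that "we will correlate change in severity of itch and pain interference with change in %BSA of treatable AD". For the arm comparison, "Two-tailed t-tests will compare changes in itch and pain interference between crisaborole and tacrolimus". For the rest, "Secondary and tertiary analyses will employ similar statistical methodology as the primary analyses but to anxiety, depression, sleep, quality of life, and caregiver burden". The section also lists ANCOVA, correlation and regression in general terms, aimed at change in itch or pain interference. EASI does not appear in it.

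**The concern.** A reader of section 1.4 expects each PRO or caregiver change to be set against change in EASI. An analyst who follows section 11.2 literally would set it against change in %BSA. The secondary and tertiary analyses borrow the primary methods, so the same substitution would carry over to them.

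Two things are at stake. First, the correlation reported would not be the one hypothesised. If the choice between EASI and %BSA is left open, it could be made after the data have been seen. Second, section 11.1 leans on two EASI results, a correlation with the PROs and a between-arm comparison, and section 11.2 specifies neither. The closing sentence of 11.1 also invites reading a non-significant EASI difference as similar clinical effectiveness.

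**Working it through.** The plan states no figure for this point, so the main check compares the text. The arithmetic then shows how the two measures differ and what the correlations can detect.

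**1. Text count.** Three of the three hypotheses in 1.4 name EASI. Section 11.2 names EASI zero times and names one clinical correlate, change in %BSA.

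**2. What each measure captures (section 5.3).** %BSA sums the affected area by the rule of nines. EASI is, for each of four regions, severity score × area score × multiplier, summed over regions. The severity score adds four signs graded 0 to 3. The multipliers sum to 1.0 in both age groups:
- 0 to 7 years: 0.2 + 0.3 + 0.2 + 0.3 = 1.0
- 8 years and over: 0.1 + 0.3 + 0.2 + 0.4 = 1.0

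**3. Worked divergence, area score 2 in every region.**
- All four signs moderate: severity 4 × 2 = 8, so EASI = 8 × 2 × 1.0 = 16.
- All four signs mild, area unchanged: severity 4 × 1 = 4, so EASI = 4 × 2 × 1.0 = 8.
- EASI halves and %BSA does not change.

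In the other direction, area score 2 spans 10% to 29%. With signs unchanged at moderate, a fall in affected area from 29% to 10% of every region, (29 − 10)/29 = 66%, leaves EASI at 16. This second case needs every region to cross almost a whole band, so it is an extreme illustration.

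**4. Detectable correlation.** With the Fisher z approximation, two-sided 0.05 and 80% power, |r| = tanh((1.960 + 0.842)/√(n − 3)). The 40 children and 20 per arm come from 11.1. Under 5.1, children under 5 give no self-report data. The documents give no age split, so 20% and 30% under 5 are assumptions.

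| Set | n | Detectable r (absolute) |
|---|---|---|
| Pooled, all | 40 | 0.43 |
| Pooled, 20% under 5 | 32 | 0.48 |
| Pooled, 30% under 5 | 28 | 0.51 |
| One arm, all | 20 | 0.59 |
| One arm, 20% under 5 | 16 | 0.65 |
| One arm, 30% under 5 | 14 | 0.69 |

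Section 11.1 counts a child as evaluable after the 6-week visit alone, so 12-week numbers may be lower.

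**5. Between-arm EASI at 20 per arm.** The documents give no SD for EASI, so widths are in SD units. The unadjusted 95% CI half-width is t(0.975, 38) × √(2/20) = 2.024 × 0.316 = 0.64 SD. With baseline adjustment and an assumed baseline-to-12-week correlation of 0.5, it is t(0.975, 37) × √(2/20) × √0.75 = 2.026 × 0.316 × 0.866 = 0.55 SD.

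**6. Collection.** The visit text in 5.1 lists EASI and ISGA at weeks 6 and 12 but not %BSA. The Assessment Forms entry in 5.3 and the schedule in section 13 list all three at every assessment. The correlate that 11.2 names is therefore the one whose follow-up collection is described inconsistently.

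**The case against.** The best defence is that 11.2 leaves room for EASI. It plans correlation and regression analyses in general terms and baseline descriptives of disease severity, and 11.1 speaks of correlation with EASI. Section 1.2 gives EASI only as an example of an objective severity measure. This has some force: a reader might infer that no EASI analysis is intended at all, and the documents do not establish that. What they do establish is that EASI is never named in 11.2 and that, where a clinical correlate is specified, it is %BSA. Section 1.4 names EASI alone, so the mismatch remains.

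A reader might also infer that EASI and %BSA move independently, so that a %BSA correlation says nothing about the hypotheses. That goes too far. EASI contains an area score, so the two are structurally linked, and a %BSA correlation is partial, indirect evidence.

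The detectable r is the same whichever correlate is used, so it does not measure the harm of choosing %BSA. It bears only on whether to pool the arms. The between-arm interval width likewise bears only on the closing sentence of 11.1.

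Finally, EASI is in no outcome tier of 1.4, and 11.1 says that superiority does not depend on it. A between-arm EASI analysis is therefore needed only if the sponsor keeps EASI in the superiority conclusion.

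**Conclusion.** The point holds as a mismatch between hypotheses and analysis plan. Followed as written, 11.2 correlates itch and pain with a related but different measure from the one in all three hypotheses. The worked example (EASI 16 to 8 with no %BSA change) shows that the measures are not interchangeable. The documents give no basis for saying how far they would diverge in this trial.

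A reader might infer that the treatment comparison is compromised. It is not: the between-arm comparisons of PROs do not use EASI or %BSA.

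Pooling needs a decision because the primary and secondary hypotheses concern changes under crisaborole. Testing within that arm raises the detectable |r| from about 0.43 to about 0.59, and further once children under 5 are excluded; by how much depends on the assumed age split. If EASI stays in the superiority statement, an unadjusted half-width of about 0.64 SD means that a non-significant difference is weak evidence of similar effectiveness.

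**What to change.** In section 11.2:

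- Make change in EASI from baseline to 12 weeks the main clinical correlate of change in itch and pain interference, and of the secondary and tertiary measures. Report each r with its 95% CI and n, and keep change in %BSA as supportive.
- State that correlations with the five child self-report measures use children aged 5 or older, while CSHQ, CBI and FDLQI use all pairs.
- State whether correlations are pooled or by arm.

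In section 11.1, state whether EASI enters the superiority conclusion. If it does, add to 11.2 a between-arm difference in EASI change, adjusted for baseline EASI, with its 95% CI. Reword the closing sentence of 11.1 so that it refers to that interval and does not treat non-significance as similar effectiveness. If it does not, remove EASI from the rule.

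Reconcile the 6- and 12-week visit text in 5.1 with 5.3 and section 13 on whether %BSA is assessed.

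Rewriting 1.4 and 11.1 around %BSA would also remove the mismatch, but it would drop sign severity from the hypotheses and rely on the less consistently described measure.

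The cost is wording and a little analysis. EASI is already collected at baseline, 6 and 12 weeks, so no visit or data item is added.

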## 3. CHARACTERISTICS OF RESEARCH POPULATION

### 3.1. Number of Subjects

This study will enroll 40 patient and caregiver pairs (i.e., 20 patients and caregivers per topical treatment; 80 subjects total). Adjusting for potential 20% withdrawal or dropout rate, we will accrue up to 48 patient and caregiver pairs. Patients must be between the ages of 2 to 15 years with mild to moderate atopic dermatitis. Caregivers must be the adult parent or guardian (18 years or older) of the eligible patient. Further discussion of sample size and power of sample can be found §11.1 on page 23.

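### Section 11.2 labels ANCOVA primary without a covariate or treatment term and gives the comparison of arms to an unranked t-test on change; the superiority rule in 11.1 cites neither

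*Combined protocol and SAP*

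**What the plan says.** Section 1.4 sets two primary outcomes, "Change in PROMIS® Itch and PROMIS® Pain Interference measures after 12 weeks of treatment", and hypothesises more improvement on crisaborole than on tacrolimus. Caregiver burden is a tertiary outcome there.

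Section 11.2 names the methods in three separate sentences:

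- "Primary analyses will use ANCOVA, correlative analyses, and regression analyses to identify significant changes in itch or pain interference from baseline to 12 weeks". No covariate, treatment term or contrast follows.
- "Longitudinal analyses will be performed to examine changes in itch and pain interference over time". No model is given.
- "Two-tailed t-tests will compare changes in itch and pain interference between crisaborole and tacrolimus". This is the only method tied to the two arms. It is not labelled primary, and no adjustment is mentioned.

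Section 11.1 gives the rule for the comparative conclusion. It says that "superiority is dependent on significant changes in PROs and their potential correlation with EASI", and then that "crisaborole would be superior to tacrolimus if crisaborole improves PROs (and/or caregiver burden"), provided that EASI does not differ significantly between the treatments. It names no test, does not say whether the change in question is within or between arms, and does not say whether one or both primary outcomes must succeed. The same section adds: "Subjects that complete at least the 6 week assessment will be considered evaluable".

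**The concern.** The trial is meant to say whether crisaborole is better than tacrolimus, but the plan does not link that conclusion to one analysis. The methods called primary are not written as a comparison of arms. The method that compares arms is not called primary. The superiority rule refers to neither.

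Two things are at stake. The first is precision. If the t-test decides because it alone mentions the arms, the trial gives up information from a baseline score that it already collects. The second is pre-specification. With two plausible between-arm tests, two primary outcomes and a tertiary outcome that may stand in for them, the deciding result could be chosen after the data are seen.

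**Working it through.** **The plan's own figure.** Section 11.1 states that 16 subjects give 80% power for a change of 4, citing an effect of 5.0 and SD 10.0 at two-sided 0.05. If that calculation matched one test, it would show which test was meant.

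- Paired change, n = (SD × (1.960 + 0.842) / δ)²: for δ = 4, n = 50; for δ = 5, n = 32.
- Two arms, per-arm n = 2 × (SD × 2.802 / δ)²: for δ = 4, n = 99; for δ = 5, n = 63.

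Neither gives 16. That number appears only under unstated readings, for example a paired test of 5 points with an SD of change of about 7.07. So the sample size section does not identify the deciding test. The mismatch itself is a separate matter.

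**Inputs for comparing the two tests.** From the documents: two-sided 0.05 (11.1, 11.2), 1:1 allocation (5.4), 20 evaluable per arm, 5 points and SD 10 (11.1). Assumed: the 5 points are a difference between arms; SD 10 applies at each visit (11.1 does not say whether it is the SD of a score or of change); the correlation r between baseline and week 12 is 0.3, 0.5 or 0.7; all 20 per arm have week-12 scores.

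**Formulas.** Variance of change = 2(1 − r)SD². Residual variance of ANCOVA on baseline = (1 − r²)SD². Their ratio is (1 + r)/2. The noncentrality is 5 / (s√(2/20)), where s is the relevant SD, with 38 degrees of freedom for the t-test and 37 for ANCOVA.

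| r | SD of change | ANCOVA SD | Variance ratio | Power, t-test | Power, ANCOVA | 95% CI half-width, t-test vs ANCOVA |
|---|---|---|---|---|---|---|
| 0.3 | √140 = 11.83 | √91 = 9.54 | 0.65 | 26% | 37% | 7.6 vs 6.1 |
| 0.5 | √100 = 10.00 | √75 = 8.66 | 0.75 | 34% | 43% | 6.4 vs 5.5 |
| 0.7 | √60 = 7.75 | √51 = 7.14 | 0.85 | 51% | 58% | 5.0 vs 4.6 |

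Simulated ANCOVA power is about one percentage point lower, because of chance imbalance at baseline.

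**Other readings of the inputs.**

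- If SD 10 is the SD of change, power at 20 per arm is 34% for the t-test against 48%, 43% and 39% for ANCOVA.
- Section 3.1 says "we will accrue up to 48 patient and caregiver pairs". With all of them contributing, 24 per arm, power is 30% vs 43%, 40% vs 50% and 59% vs 66%.
- Children under 5 give no primary outcome data (5.1). If ages 2 to 15 were evenly represented, 20 × 11/14 = 15.7 per arm would contribute. At 16 per arm, power is 21% vs 30%, 28% vs 35% and 42% vs 48%. Children seen at week 6 only would lower it further.

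**Consequence of choosing between the tests.** The simulations used bivariate normal scores and 20 per arm, with 400,000 trials per r under no difference. Each test alone has 5.0% type I error. If a claim is made whenever either is significant, the error on one outcome is 7.7%, 7.3% and 6.8%. With a true 5-point difference (200,000 trials per r), the two tests give different verdicts in 20%, 17% and 14% of trials.

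**Two outcomes, a separate source.** With ANCOVA alone and either primary outcome allowed to count unadjusted, the error is 8.8% to 9.8% for correlations between the outcomes of 0.6 down to 0. For independent outcomes, 1 − 0.95² = 9.75%.

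**The case against.** The best defence is that 11.2 already divides the work: ANCOVA, correlation and regression describe change from baseline, and the t-test compares the arms. The t-test fits a primary outcome defined as change, and its level is fixed. Preferring ANCOVA is then a choice of efficiency.

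Much of this stands, and it rules out several stronger readings that a reader might infer.

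- *The plan has no between-arm test.* It has one. What is missing is its rank and any link to the superiority rule.
- *The ANCOVA has no response.* The outcome and the time window are given. Only change versus week-12 score is open, and with baseline as covariate both give the same treatment estimate.
- *The t-test is wrong.* It is a valid test of the difference in change, only less precise.
- *The plan's type I error exceeds 5%.* The 7% to 8% arises only if the favourable test is picked, and nothing in the documents says that it will be. Adding the free choice of outcome gives 12% to 15%, but most of that excess comes from the missing multiplicity rule.
- *Baseline scores are taken after allocation is known, so change is biased.* Sections 5.1 and 13 do not require baseline measures before allocation is revealed, but they do not say that the reverse happens. That is a question of conduct, to be raised separately.

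The defence does not dispose of the rest. If the t-test decides, the analyses labelled primary do not, and 11.1 still refers to neither.

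**Conclusion.** The point holds as a gap in specification joined to a loss of precision that can be avoided at almost no cost. The plan should be changed, but its listed tests are not invalid.

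Baseline-adjusted ANCOVA has 65% to 85% of the variance of the change-score comparison for r from 0.3 to 0.7. At 20 per arm that is worth about 7 to 11 percentage points of power for a 5-point difference. These figures rest on SD 10 per visit and on values of r that the documents do not supply. The direction does not depend on them: (1 + r)/2 is below 1 for any r below 1.

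ANCOVA is not a cure for the sample size. At r = 0.5 the normal formula asks for 48 per arm with ANCOVA and 63 with the t-test to reach 80% power, against 20 planned.

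**What to change.** In 11.2, state that the deciding between-arm analysis for each primary outcome is ANCOVA of the week-12 score on treatment, with the baseline score as covariate, reporting the adjusted difference and its 95% CI. State that t-tests on change and the correlative, regression and longitudinal analyses are supportive.

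In 11.1, tie superiority to that analysis. Require either both primary outcomes at 0.05, or at least one after Holm adjustment, and say which. Take caregiver burden out of the deciding rule.

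Children with a week-6 but no week-12 score count as evaluable under 11.1 but cannot enter the week-12 ANCOVA. Include them in a sensitivity analysis: a longitudinal model with the same baseline covariate and a week-12 treatment contrast.

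The cost is a few sentences and one degree of freedom. No new data, visits or staff are needed.
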